[name] student, licensed psychologist, has clinical experience from working with anxiety disorders as well as experience of clinical research. [name] will be the study-coordinator, and she will be involved in several parts of the trial (i.e., recruitment, assessment, running groups, data collection, data-analysis, and report writing).

Study site

The project take place at the Department of Global Health at Karolinska Institutet, located [name], Sweden.

Background

Objective

The current project aims to expand the evidence of prevention of anxiety disorders in children. We will take a novel approach to prevent childhood anxiety disorders by evaluating the Confident Parents - Brave Children (CPBC) program, a parent program targeting anxious parents, in a randomised controlled trial (RCT).

Research questions

- Is the CPBC-program effective in preventing childhood anxiety disorders within a period of 12 and 36 months respectively, compared to a self-help parenting book?
- Is the CPBC-program effective in preventing childhood anxiety symptoms within a period of 12 and 36 months respectively, compared to a self-help parenting book?
- Is the effect moderated by severity of parental anxiety, child anxiety symptoms at baseline, or gender or age of the child?
- Is the CPBC effective in increasing parental self-efficacy?
- Is the effect of CPBC-program mediated by changes in parental criticism and rejection, overprotection, parental modelling of anxiety or parental accommodation?
- Is the CPBC-program cost-effective?

Method

Participants

Study participants will be parents with elevated anxiety living in Sweden. Children aged 5-9, who do not meet criteria for anxiety disorder, will be included in the study together with their parents.

Sample size

To have an 80% power to detect a significant ($p \leq 0.05$) small to moderate difference (standardized mean difference = 0.4) the investigators will need to recruit 194 children. Given an anticipated attrition of 10%, the investigators will aim at including a total of 216 children. Participants will be recruited through advertisements. The participants will be randomly allocated to either (1) CPBC-program or (2) reading a self-help book.

Inclusion criteria:

- The parent suffers from exaggerated worry or anxiety
- The parent speaks and reads Swedish
- The child is 5-9 years old
- The child receives a clinicians assigned clinical severity rating (CSR) of 1 to 3 on anxiety disorders in ADIS-C (subclinical symptoms of anxiety)

Exclusion criteria:

- Current or recent parental alcohol or substance abuse

- The parent suffers from severe psychiatric conditions (e.g. current or recent psychotic or manic/hypomanic symptoms, severe depression or increased risk of suicide)
- Social conditions that would obstruct from participation (e.g. ongoing custody dispute, domestic violence, ongoing investigation of child neglect through social services)
- The child suffers from/is currently in treatment for an anxiety disorder or depression
- The child is currently undergoing a neuropsychological evaluation
- The child has no symptoms of anxiety at all (the child receives a clinicians assigned CSR of 0 on all anxiety disorders in the ADIS-C interview)
- The child meets criteria for an anxiety disorder (the child receives a clinicians assigned CSR of 4 or above on any anxiety disorder in ADIS-C interview)

Procedure

Recruitment of study participants will be done through advertisements in local newspapers and on Facebook. Interested parents will be able to read more about the study at Karolinska Institutets webpage and to complete a screening questionnaire online. All parents who have answered the screening questions will be contacted by email. Those eligible will be booked for a short phone interview to further screen for eligibility according to the inclusion and exclusion criteria. Parents who clearly meet exclusion criteria will be excluded after the phone screening interview, while those who are still judged to be eligible participants are invited to a diagnostic assessment via a video conferencing application (Zoom).

[figure not shown]
Before the video assessment, potential participating parents and children will be provided with both written and oral information about the study. If willing to participate, we will collect written informed consents from the parents and oral informed consents from the children. Oral consents from children will be collected during the video conferencing call. During the video call, parents will answer questions about their own and their children's mental health. A licensed psychologist will administer two semi-structured diagnostic interviews (M.I.N.I. and ADIS) to collect information about anxiety disorders as well as other psychiatric disorders. After the diagnostic video interview, the research team will decide if the parents meet inclusion criteria or not.

Parents who are included will receive an email with personal login information to a battery of questionnaires (baseline assessment). The parents are then randomly assigned to either (1) the intervention group, *Confident Parents - Brave Children* (CPBT) or (2) the active comparator group (reading a self-help book).

The CPBT will contain 6 group sessions during a period of 10 weeks. Individual booster sessions with all participants will be scheduled one month after the last group session. All group leaders will be licensed psychologists.

At the end of the intervention phase (after the booster session), the participants will receive an email with personal login information to complete a battery of questionnaires (post assessment).

Follow-up, semi-structured diagnostic interviews are conducted 12- and 36-month post-treatment. The participants will also complete a battery of questionnaires at 12- and 36-month follow-ups. An overview of the study is provided in figure 1 below.

Measures

Primary outcome measure

The primary outcome will be change in severity of childhood anxiety disorder, as rated by clinician at 12- and 36-months follow-up. Clinical Severity Ratings (CSR) range from 0 to 8, where a value of 4 and higher indicate that the child meets criteria for an anxiety disorder. The CSR is extracted from the Anxiety Disorders Interview Schedule - Schedule for Children (ADIS-C). The CSR is rated by clinician based on interviewing with primary caregiver.

Secondary outcome measures - parent reported

EQ5D

EQ5D is a validated self-rated questionnaire of the parent's quality of life, including 5 items (each item scored 1-3 where lower scores indicates better quality of life). EQ5D will be used in the cost-effectiveness analysis and measures changes in health-related quality of life (HRQoL) in parents on five dimensions: mobility, self-care, usual activities, pain/discomfort, and anxiety/depression

Time frame: Base-line assessment, post-intervention, 12 month follow-up, 36 month follow-up.

Child Health Utility 9D (CHU9D)

CHU9D is a validated parent-rated questionnaire of the child's quality of life, including 9 items (each item scored 1-5 where lower scores indicates better quality of life).

Time frame: Base-line assessment, post-intervention, 12 month follow-up, 36 month follow-up.

Expressed Emotion Adjective Checklist (EEAC)

The EEAC is a validated self-rated questionnaire of the parent's positive and negative emotions directed towards the child. The EEAC include 20 adjectives (each scored 1-8 where 1 indicates never and 8 always).

Time frame: Base-line assessment, post-intervention, 12 month follow-up, 36 month follow-up.

Revised Parental Overprotective Scale (RPOS)

RPOS is a revised version of the validated self-rated questionnaire of the parent's overprotective behaviors, including 11 items (each item scored 1-5 where higher scores indicates more overprotective behaviors).

Time frame: RPOS at post-intervention, 12-month, and 36 month follow-up.

Modelling of Parental Anxiety Questionnaire (MPAQ)

MPAQ is a self-rated questionnaire of the parent's modelling of anxious and non-anxious behaviors (two different sub-scales), including 7+9 items (each item scored 1-5 where higher scores indicates more modelling).

Time Frame: Base-line assessment, post-intervention, 12 month follow-up, 36 month follow-up.

Screen for Child Anxiety Related Disorders Revised (SCARED-R)

SCARED-R is a validated parent-rated questionnaire of the child's anxiety symptoms including 41 items (each item scored 0-2 where higher scores indicates more anxiety symptoms).

Time frame: Base-line assessment, post-intervention, 12 month follow-up, 36 month follow-up.

Patient Health Questionnaire (PHQ-9)

PHQ-9 is a validated self-rated questionnaire of the parent's depression symptoms, including 9 items, (each item scored 0-3 where higher scores indicates more depressive symptoms).

Time frame: Base-line assessment, post-intervention, 12 month follow-up, 36 month follow-up.

PROMIS-Anxiety Short Form

The PROMIS Anxiety Short Form is a validated self-rated questionnaire of the parent's anxiety symptoms, including 8 items, (each item scored 1-5 where higher scores indicates more anxiety symptoms).

Time Frame: Base-line assessment, post-intervention, 12 month follow-up, 36 month follow-up.

Family Accommodation Scale-Anxiety Parent Report (FASA-PR)

The FASA-PR is a validated self-rated questionnaire of the parent's accommodation to the child's anxiety, including 13 items (each item scored 0-4 where higher scores indicates more accommodation).

Time frame: Base-line assessment, post-intervention, 12 month follow-up, 36 month follow-up.

Parenting Sense of Competence Scale (PSOC)

PSOC is a validated self-reported questionnaire of the parent's sense of competence, including 11 items (each item scored 1-6 where higher scores indicates more sense of competence).

Time Frame: Base-line assessment, post-intervention, 12 month follow-up, 36 month follow-up.

The Trimbos/iMTA questionnaire for Costs associated with Psychiatric Illness (TiC-P)

The TiC-P is a measure aimed at assessing resource use and other costs associated with psychiatric or behavioral conditions. It includes questions on healthcare social support, social support parental absence from work, absence from school and productivity loss in school.

Assessment points

Participants will be assessed at pretreatment, baseline, post intervention and at 12- and 36-month follow-up.

Timeline \ Measure	Online screening	Phone screening	Video assessment	Base-line measures	Post measures	12-moth follow-up	36-month follow-up
Clinician assessed							
Demographic data	X						
ADIS			X			X	X
MINI			X				
Child CSR			X			X	X
Parent CSR			X				
Parent reported							
EQ5D				X	x	X	x
EEAC				X	x	X	x
RPOS				x	X	x	X
MPAQ				X	X	x	X
SCARED-R				X	X	x	X
PHQ-9	x				X	x	X
PROMIS Anxiety short form	x				X	X	x
FASA-PR				X	x	X	x
PSOC				X	x	X	x
CHUD-9				x	x	x	x

Table 2. Overview of measures and time points.

Intervention

Intervention (CPBT)

Previous research on parenting styles involved in the transmission of anxiety between the parent and the child could be summarized into three main themes: (1) criticism and low warmth, (2) overprotection, (3) modelling anxiety and avoidance and (4) accommodation of anxiety.

We hypothesize that helping parents gain more knowledge of childhood anxiety and use more positive parenting skills would produce warmer parenting and more acceptance of the child. We hypothesize that helping parents understand the consequences of overprotective behaviour and find opportunities to help their child in challenging/approaching behaviour would increase the autonomy of their child. We believe that helping parents challenge their own fears and remember to reward their child for approaching behaviours would increase modelling and reinforcement of approaching behaviours. Subsequently, we hypothesize that parental warmth and acceptance, increased autonomy of the child, and modelling and reinforcement of approaching behaviour would, in the long term, decrease the risk of developing an anxiety disorder. CPBT comprise six 120-minute group sessions and one individual booster sessions. All sessions will be carried out using Zoom.

Participants in the active control group will receive a parenting book containing research-based strategies for handling children's anxiety [12]. They will be instructed to read the book within the 10 weeks from baseline to post assessments but will receive no other guidelines. They will not receive any help from the research team while working with the book.

Efficacy: Data-Analysis

The efficacy of the CPBT will be evaluated in a series of regression analyses. The primary outcome measure (child CSR) will be evaluated in a generalized linear mixed model (GLMM). The measures EEAC, OP, FASA-PR and MPAQ will be evaluated separately as dependent variables using the linear mixed model (LMM).

Cost-Effectiveness

Two types of analyses (cost-utility analysis and cost consequence analysis) will be performed. The cost-utility analysis will be expressed as an incremental cost effectiveness ratio given as the difference in costs divided by the difference in quality-adjusted life years (QALYs) for parents and children between the two conditions (i.e. the cost for one additional life year with full health gained). In the cost-consequence analysis, incremental costs and outcomes per parent and /child between the conditions will be presented for each cost and outcome item. Costs in both trial arms will be estimated from a limited societal perspective. Costs will be calculated for each participant based on resource items and associated relevant unit costs. Costs to deliver the intervention will be estimated based on practitioners' time to

deliver the intervention, costs for materials, etc., using a micro-costing framework. The use of other societal resources by children and their parents will be collected at baseline and at 12 months follow-up. This comprises information on the use of resources related to healthcare and productivity losses due to absence from school for children, and productivity losses due to absence from work for parents, which will be collected using an adapted version of the questionnaire on healthcare consumption and productivity losses (TiC-P) [29]. The TiC-P is a feasible and reliable instrument for collecting data on medical consumption and productivity losses in individuals with mild to moderate mental health problems. Total costs will be aggregated by trial arm.

As the economic data are likely to be missing at random, multiple imputation methods will be used in the base case analysis. Total QALY gains for parents and children over the trial period will be estimated using the area under the curve method. Cost data and QALYs will be analyzed using generalized linear models (GLM) to account for non-normal distribution. The GLM approaches allow the consideration of other distributions and functional forms to fit the costs data. Data will be analyzed while controlling for covariates and adjusting for baseline values.

Safety procedures and adverse events

If a child meets criteria for an anxiety disorder when the first diagnostic interview is carried out, the family is excluded and referred to health care. If the parent suffers from substance or alcohol abuse or severe psychiatric illness, or in case of domestic violence, the family will be excluded and referred to health care or social services.

Parents and children are free to seek care for mental health problems while participating in the study. Only licensed psychologists will carry out the diagnostic assessments and be responsible for leading the parenting groups. To prevent any possible concern about data safety among the participants, there will be information on how data is securely handled. All participant data will be handled confidentially. Data will be imported to a coded data file and the investigators will perform all analysis.

In case of an adverse event, the members of the research team will inform the study coordinator ([name]) who will be responsible for deciding what actions are appropriate to take. Any adverse events will be described in the planned publication.

Project schedule

Spring 2021: Recruitment and assessment of cohort 1

Fall 2021: Recruitment and assessment of cohort 2

Spring 2022: Recruitment and assessment of cohort 3, and follow up cohort 1

Fall 2022: Follow up cohort 2

Spring 2023: Follow up cohort 3

Summer-fall 2023: Publishing results

Presentation of results

The study results will be presented in several articles submitted for publication in scientific journals.

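### The 80% power claim makes no allowance for therapy-group clustering in the CPBC arm, although only that arm is treated in groups

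*Protocol*

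**What the plan says.** **Randomisation.** The Sample size section allocates participants individually: "The participants will be randomly allocated to either (1) CPBC-program or (2) reading a self-help book". No ratio is given.

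**Delivery.** Under Procedure, "The CPBT will contain 6 group sessions during a period of 10 weeks" (the protocol uses CPBC and CPBT for the same programme). Licensed psychologists lead the groups. One individual booster session follows a month after the last group session. The Intervention section says that control families get a parenting book, are told to read it within the 10 weeks, and have no support from the research team.

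**Sample size.** The inputs are a standardised difference of 0.4, p ≤ 0.05 and 80% power, from which "the investigators will need to recruit 194 children". Then: "Given an anticipated attrition of 10%, the investigators will aim at including a total of 216 children". No group size, number of groups, ICC or design effect appears.

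**Analysis.** The Efficacy section says "The primary outcome measure (child CSR) will be evaluated in a generalized linear mixed model (GLMM"), and names linear mixed models for four parent measures. It lists no fixed or random effects for any of these models.

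**The concern.** Families in one CPBC group share leaders, fellow parents and six two-hour sessions. Randomising families individually does not remove correlation that arises afterwards from shared treatment. Book families have no such shared exposure, so clustering, if present, affects one arm only.

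Two things are at stake. First, positive correlation enlarges the variance of the CPBC arm mean, so the planned number of children gives less power than the protocol states. A correct model later on would give valid standard errors but would not restore that power. Second, an analysis that ignored the group would understate the standard error of the treatment difference. The first follows from figures that the protocol fixes, once some correlation exists. The second depends on model details that the protocol does not give.

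**Working it through.** **Inputs from the protocol:** standardised difference 0.4 (SD = 1), alpha 0.05, power 80%, 194 evaluable, 10% attrition, 216 enrolled.

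**Assumptions:** two-sided test (one-sided would need only 156 in total, far from 194); 1:1 allocation, so n = 97 per arm; m = 6 to 12 evaluable families per group; ICC = 0.01 to 0.10.

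**Step 1: reproduce the stated figure with independent children.**

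- Required n per arm = 2 × [(1.960 + 0.842)/0.4]² ≈ 98.1, rounded up to 99, or 198 in total. The stated 194 is within 3% of this.
- Power at 97 per arm: SE = √(2/97) = 0.1436; Φ(0.4/0.1436 − 1.96) = 79.6%.
- Attrition: 194/0.9 = 215.6, rounded up to 216.

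So 194 is an independent-data figure, and the step up to 216 is used entirely for attrition. Nothing is left for clustering.

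**Step 2: partially nested design.** With total variance 1 in both arms and clustering in CPBC only:

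- DE = 1 + (m − 1) × ICC
- Var(difference) = (DE + 1)/97
- Power = Φ(0.4/√Var − 1.96)

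For m = 8 and ICC 0.05: DE = 1.35; Var = 2.35/97 = 0.02423; SE = 0.1556; 0.4/0.1556 = 2.570; power = Φ(0.610) = 72.9%.

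**Step 3: type I error if the group were ignored.** The true SE exceeds the model SE by the ratio R = √[(DE + 1)/2], and the two-sided error is 2 × [1 − Φ(1.96/R)]. For m = 8 and ICC 0.05: R = 1.084, error = 7.1%.

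| m | ICC | DE | Power (z) | Power (Satterthwaite df) | Type I error if group ignored | Evaluable N for 80% |
|---|---|---|---|---|---|---|
| 6 | 0.01 | 1.05 | 78.6% | 77.0% | 5.3% | 202 |
| 8 | 0.02 | 1.14 | 76.8% | 74.6% | 5.8% | 210 |
| 8 | 0.05 | 1.35 | 72.9% | 70.2% | 7.1% | 232 |
| 12 | 0.10 | 2.10 | 60.9% | 55.4% | 11.5% | 306 |

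The last column is unadjusted: 2 × (DE + 1) × (2.802/0.4)², with the per-arm number rounded up. The Satterthwaite column takes 97/m groups in the CPBC arm.

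**Step 4: recovery from baseline adjustment.** Let r be the assumed correlation between baseline and follow-up CSR, and multiply Var by (1 − r²).

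- m = 8, ICC 0.05, r = 0.3: Var = 0.91 × 0.02423 = 0.02205; power ≈ 77%.
- m = 8, ICC 0.02, r = 0.3: Var = 0.91 × 2.14/97 = 0.02008; power ≈ 81%.
- m = 8, ICC 0.05, r = 0.4: Var = 0.84 × 0.02423 = 0.02035; power ≈ 80%.

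This scales the between-group variance as well. If baseline explains only variation within groups, Var at ICC 0.05 and r = 0.3 is [(0.40 + 0.95 − 0.09) + 0.91]/97 = 0.02237 and power is about 76%, so the conclusion is the same.

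**The case against.** **Standard errors.** A reader might infer that the planned standard errors will be too small. The protocol does not support that. It lists no terms at all for its mixed models, such a model can carry a therapy-group effect, and random-effect structure is commonly left to an analysis plan, which is not available here. The type I figures apply only if the group is omitted and the ICC is positive.

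**Direction.** A reader might also infer that ignoring the group would favour CPBC. It would not. Under the null hypothesis the excess false positives fall equally on both sides, so false findings for the book rise just as much.

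**Size of the power loss.** Nothing in the protocol supports a particular ICC. The primary outcome is a clinician's rating of the child at 12 and 36 months, the groups are for parents, and each CPBC participant also has an individual booster. A low ICC is plausible, and at ICC 0.01 with 6 per group the loss from clustering is one point (79.6% to 78.6%). This stands as a limit on the size. It does not show that the correlation is zero.

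**Unadjusted figures.** The outcome is change in CSR, baseline CSR is available, and a mixed model is planned, so an unadjusted calculation may understate the power of the eventual analysis. This stands in part. The correlations in Step 4 are assumed, and entry is restricted to CSR 1 to 3, which could weaken the baseline correlation.

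**Conclusion.** The point holds for the sample size. The figure of 194 assumes independent children, and it sits at 79.6% power before any clustering is considered. For an unadjusted comparison, any positive within-group correlation takes it further below the stated 80%.

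The size is conditional. Under 1:1 allocation, 6 to 12 families per group and ICC 0.01 to 0.10, power is about 79% down to 61% by the normal approximation, and about 77% to 55% with small-sample degrees of freedom. The middle case of 8 per group at ICC 0.05 gives 73% (70% with small-sample degrees of freedom).

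The analysis side is a conditional risk, since the model terms are unstated: two-sided type I error of about 5.3% to 11.5% over the same range if the group is left out.

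Severity is moderate. The group size and ICC are assumptions, baseline adjustment can recover much of the loss, and the enrolment target need not change.

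**What to change.** - Keep the enrolment target of 216. Replace the 80% statement with the power under a declared group size, ICC and allocation ratio, preferably over a short range of ICCs.
- Record a therapy-group identifier for every CPBC family while the groups run, as it may be hard to reconstruct later.
- Specify, in the protocol or the analysis plan, a random group effect in the CPBC arm only (book families as singletons) for the CSR model and the parent-measure models, with small-sample degrees of freedom.
- Adjust the CSR model for the baseline CSR already collected at the video assessment. With an assumed r of 0.3 and 8 per group, power is about 77% at ICC 0.05 and about 81% at ICC 0.02 (normal approximation).

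**Cost.** Analysis wording and one extra recorded variable; no change to treatment or recruitment. The stated power becomes slightly less favourable and the intervals slightly wider.

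### Resource use is not collected at the post assessment, so non-delivery costs to the 12-month visit are complete only if one form recalls 14 to 15 months

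*Protocol*

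**What the plan says.** The schedule for resource use is set in one sentence of the protocol's Cost-Effectiveness section: "The use of other societal resources by children and their parents will be collected at baseline and at 12 months follow-up". The TiC-P entry under Measures describes the content ("It includes questions on healthcare social support, social support parental absence from work, absence from school and productivity loss in school") but gives no time points, and Table 2 has no TiC-P row. No recall window is given anywhere in the protocol. The costs are then summed: "Total costs will be aggregated by trial arm".

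The Procedure section fixes the calendar. Parents complete the baseline battery and are randomised afterwards. "The CPBT will contain 6 group sessions during a period of 10 weeks", and "Individual booster sessions with all participants will be scheduled one month after the last group session". The post battery follows: "At the end of the intervention phase (after the booster session), the participants will receive an email". The text on the control arm, under Intervention, instead puts the post assessment 10 weeks from baseline. Later visits are counted from the end of treatment: "Follow-up, semi-structured diagnostic interviews are conducted 12- and 36-month post-treatment".

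On the outcome side, the Measures section and Table 2 place EQ5D and CHU9D at baseline, post, 12 months and 36 months. QALYs are computed as an area under the curve. The cost of delivering the intervention is estimated separately, by micro-costing of practitioner time and materials.

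**The concern.** The baseline TiC-P describes use before randomisation. It can serve as a covariate, but it adds nothing to trial-period costs. That leaves one retrospective form to cover the whole span from baseline to the 12-month visit, and that span is longer than a year because the visit is counted from post-treatment.

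The cost-utility ratio divides a difference in costs by a difference in QALYs. If the 12-month form looks back a year or less, the QALY curve includes the weeks of group sessions and reading, with a measured point at their end, while healthcare use and absence from work and school in those weeks are not observed. The planned multiple imputation fills in forms that were not returned. It cannot supply a period that no form asks about.

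This point concerns costs up to the 12-month visit only. Limiting the economic analysis to that visit would not remove it.

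**Working it through.** The protocol gives no figure for cost coverage, so there is none to reproduce. The check is calendar arithmetic.

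**Inputs**
- Group phase: 10 weeks (Procedure). One month = 365.25/12 = 30.44 days, so 70/30.44 = 2.30 months.
- Booster: one month after the last group session (Procedure).
- Post assessment: at 10 weeks (control-arm text under Intervention) or after the booster (Procedure). Both are carried through.
- 12-month visit: 12 months after post-treatment (Procedure), taken as 12 months after the post assessment.
- Recall window *r* of the TiC-P: not stated. Windows of 3, 6 and 12 months are assumptions, with recall back to baseline as the limiting case.
- The groups are taken to start at about baseline.

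**Interval from baseline to the 12-month visit**
- Post at 10 weeks: 2.30 + 12 = 14.30 months.
- Post after the booster: 2.30 + 1 + 12 = 15.30 months.

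**Coverage by the 12-month form**, min(*r*, interval) / interval

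| Recall window | Interval 14.30 | Interval 15.30 | Months not observed |
|---|---|---|---|
| 3 months | 3/14.30 = 21.0% | 3/15.30 = 19.6% | 11.3 to 12.3 |
| 6 months | 6/14.30 = 42.0% | 6/15.30 = 39.2% | 8.3 to 9.3 |
| 12 months | 12/14.30 = 83.9% | 12/15.30 = 78.4% | 2.3 to 3.3 |
| Back to baseline | 100% | 100% | 0 |

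**Which months are lost.** A window of 12 months, counted back from a visit 12 months after post, reaches post and no further. The group phase lies before post under both timings, so none of it is observed with any window of 12 months or less. A later start of the groups would lengthen the gap, not close it. A window between 12 months and the full interval recovers part of the early period.

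**With a TiC-P form added at post**, [min(*r*, baseline to post) + min(*r*, 12)] / interval
- 3-month window: (2.30 + 3)/14.30 = 37.1%, or (3 + 3)/15.30 = 39.2%.
- 6-month window: (2.30 + 6)/14.30 = 58.0%, or (3.30 + 6)/15.30 = 60.8%.
- 12-month window, or wording that runs from the last questionnaire: (2.30 + 12)/14.30 = 100%, or (3.30 + 12)/15.30 = 100%.

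The added form therefore closes the gap only if the two forms are worded to join. Under a short fixed window it narrows the gap and no more.

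**The case against.** The strongest reply is that nothing in the protocol is false here. The TiC-P is an adapted version, its recall window is unstated, and a window reaching back to baseline is not excluded. Such detail may sit in an analysis plan or health-economic plan that is not at hand. A reader might infer from the schedule that total costs to the 12-month visit cannot be derived at all. The documents do not support that: a single 12-month form asking about the time since baseline would cover the whole interval with no added form, and a shorter window could be extrapolated.

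A reader might also infer that the cost difference between arms is biased. That is not shown either. The percentages above are shares of calendar time, not of cost. The main cost that differs by arm in the early months is delivery, which is micro-costed. Parental time in sessions or reading is not a listed TiC-P item unless it leads to absence from work. The protocol expects the reduction in disorder risk in the long term, so differences in care use may well arise later, within reach of the 12-month form.

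These replies limit the point but do not remove it. The schedule is a data-collection decision written in this protocol, and a later plan can extrapolate but cannot create observations. Under the stated schedule each option has a price: 12 months or less leaves the group phase unobserved, and more than 12 months relies on parents recalling visits and absences from over a year ago. The missing Table 2 row and the unstated window would not be findings by themselves.

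**Conclusion.** The point holds as a weakness in the collection schedule that is cheap to remedy. Non-delivery costs from baseline to the 12-month visit are complete only if one form recalls 14 to 15 months. With any window of 12 months or less, at least the first 2.3 to 3.3 months go unobserved, including the 10-week group phase. For assumed windows of 3, 6 and 12 months the form sees about 20-21%, 39-42% and 78-84% of the interval.

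This rests on the Procedure section's counting of follow-up from post-treatment and on the assumed windows. The ranges reflect the two descriptions of when the post assessment takes place. The effect on the incremental cost, in size or direction, cannot be worked out from the documents.

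**What to change.** Add the TiC-P to the online post battery, and give it a row in Table 2 at baseline, post and 12 months. Word the post and 12-month forms to ask about the time since the last questionnaire. The post form then covers 2.3 to 3.3 months and the 12-month form about 12 months, so together they run from baseline to the 12-month visit without gap or overlap.

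If a shorter fixed window is kept, or if the post assessment has already passed for some cohorts, state the window in the Cost-Effectiveness section, say that costs for the unobserved months are extrapolated from it, and test that in a sensitivity analysis.

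The cost is one more questionnaire in a battery that parents already complete online, so a few minutes each at post. The 12-month form would still ask for about 12 months of recall, which carries some recall error.
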